- 3. A score of 20 or more on the Adult ADHD Investigator Symptom Report Scale (AISRS), and, for those individuals stably treated with stimulants, a CGI-ADHD severity score of no greater than 4 ("moderately ill").
 - i. Subjects on a stable dose of stimulant medication must be treated on the same dose for at least 1 month prior to study entry.

Exclusion Criteria:

- 1. A history of intolerance to magnesium supplementation, or the ingredients in MMFS202 (6-hour release) AND MMFS302 (12-hour release).
- 2. Pregnant or nursing females.
- 3. A known unstable medical illness including hepatic, renal, gastroenterological, respiratory, cardiovascular (including hypertension ≥ 140/90 mmHg at screening), endocrinologic (e.g. thyroid), neurologic (e.g. seizure), immunologic, hematologic, or psychiatric (other than ADHD) disorder. Individuals with kidney dysfunction will be excluded, as dysfunctional kidneys may have difficulty clearing the magnesium from the body (which can result in dangerously high magnesium levels). Individuals with heart block will be excluded from the study.
- 4. Any medical condition that the Principal Investigator (PI) believes will be exacerbated by study participation.
- 5. A history of cancer (except localized skin cancer without metastases or *in situ* cervical cancer) within 5 years prior to screening.
- 6. A known history of narrow-angle glaucoma.
- 7. Current (within 3 months) DSM-V criteria for abuse or dependence with any psychoactive substance other than nicotine.
- 8. IQ<80 (based on the Wechsler Abbreviated Scale of Intelligence-II Full Scale IQ calculation)
- 9. Multiple adverse drug reactions.
- 10. Any other concomitant medication with primarily central nervous system activity as specified in Concomitant Medication portion of the protocol.
- 11. Current use of MAO Inhibitor or use within the past two weeks.
- 12. Current use of antibiotics, as the study agent may reduce the absorption of antibiotics.
- 13. Subjects may not take any of the following substances for at least 7 days prior to baseline and throughout the study:
 - a. Calcium channel blockers including:
 - i. Felodipine (Plendil®)
 - ii. Amlodipine besylate (Norvasc®).
 - b. Any psychoactive medications including:
 - i. Antipsychotics
 - ii. Anxiolytics
 - iii. Antidepressants
 - c. Any medications known to interact with magnesium including:

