Informed consent will be obtained prior to the performance of any protocol procedures and prior to administration of study drug. The informed consent document will be used to explain in simple terms the risks and benefits of study participation to the subject. The nature of the study will be fully explained to the subject by a board-certified physician who is either the primary investigator or a co-investigator. The subject will be encouraged to ask questions pertaining to their participation in the study and the subject may take as much time as they feel is necessary to consider his/her participation in the study as well as consult with family members or their physicians. Participation in this study is voluntary and the subjects may withdraw from the study at any time. The IRB-approved informed consent documents will be signed and dated by the subject and the physician obtaining consent.

V. STUDY PROCEDURES

We will conduct a 12-week open label pilot clinical trial exploring the cognitive effects and tolerability of L-Threonic acid Magnesium salt in adults with ADHD. We will recruit up to 25 subjects, and enrollment will stop once 15 subjects are expected to complete the study.

After providing study information and obtaining IRB approved informed consent, participants will undergo a comprehensive assessment including a psychiatric assessment reviewing current and lifetime DSM-V Axis I conditions, medical history including history of any cardiac symptoms or abnormalities reported on routine clinical exams, and a neuropsychological evaluation which will include confirmation of an IQ greater than 80 (which can be completed at the screening or baseline visit for scheduling flexibility). If a subject has never had a cardiac physical exam a clinician will conduct one. The information obtained at this visit will be reviewed to assure that all inclusion and exclusion criteria are met prior to receiving study agent at the baseline visit. Subjects who do not meet all the criteria for enrollment after these assessments will be discontinued.

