Vital signs (blood pressure, pulse, weight) will be measured at every in-office visit. Height will be measured at baseline and at the end of the study. A urine drug screen will be performed at screening, week 6, and week 12. If the participant is found to have taken an illicit drug, he/she will have a discussion with the doctor to determine if he/she can be in the study. Subjects will be discontinued if there is suspicion of ongoing substance use. For safety purposes, an EKG will be conducted during screening and at the endpoint of the study. Females who are able to have children will also have a urine pregnancy test at screening, week 6, and week 12.

If a participant has a positive pregnancy test she will not be able to take part in the study. Female subjects of childbearing potential must agree to use a medically acceptable form of birth control (such as male for female condoms with or without spermicidal agent, diaphragm or cervical cap with spermicide, medically prescribed IUD, hormonal contraceptives like birth control pills, or abstinence) while they are receiving study agent and for 1 month after the last dose of study agent. In the event that a subject becomes pregnant, we will ask the subject's permission to obtain information about the outcome of the pregnancy and the condition of the newborn. Those subjects who terminate study participation before the completion of the study will be asked to complete all tasks scheduled to take place on the final study visit at the time of study discontinuation.

We will draw blood samples at the screening visit and at study endpoint to determine erythrocyte (red blood cell or RBC) levels of magnesium and calcium. Samples will be analyzed by LabCorp through services provided by the Harvard Clinical and Translational Science Center. Each sample volume will be approximately 3 teaspoons, for a total of 6 teaspoons drawn over the entire study.

All efforts will be made to protect subject privacy, and samples will be labeled with codenames and medical record numbers. The sponsor will not have access to information that identifies participants' samples. Results from laboratory testing (i.e. laboratory values) may become a part of the subjects' MGH medical records, however no information regarding participation in the study will become a part of the medical record.

Subject Visits:

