L-Threonic acid Magnesium salt will be provided as MMFS202 (6-hour release) and MMFS302 (12-hour release). Neurocentria, the makers of MMFS202 (6-hour release) and MMFS302 (12-hour release), will provide a detailed Certificate of Analysis attesting to the contents of the product.

Neurocentria-has provided the following list of ingredients for MMFS202 (6-hour release) and MMFS302 (12-hour release):

- Inactive ingredients: polyvinyl pyrolidone, microcrystalline cellulose, silicon dioxide, talc, and magnesium stearate

Both MMFS202 (6-hour release) and MMFS302 (12-hour release) will be provided in 0.5-gram tablets. Participants will be instructed to take one tablet of MMFS302 (12-hour release) in the morning and one tablet of MMFS202 (6-hour release) in the evening for one week 2 hours before bedtime. After one week, if well tolerated subjects will start a regimen of two tablets of MMFS302 (12-hour release) in the morning and two of MMFS202 (6-hour release) in the evening. Therefore, subjects will take up to 2 grams per day of L-Threonic acid Magnesium salt during the course of the study. However, study agent dosing will be flexible. If individual subjects display patterns of adverse effects or drug effects that suggest an alternative dosing schedule would be preferred, this will be allowed, including dose reduction to only one of either MMFS202 (6-hour release) or MMFS302 (12-hour release). The study clinician can increase or decrease the dose based on tolerability and reinstate higher doses after a decrease if tolerability increases. No subject will take more than two MMFS202 (6-hour release) or more than two tablets at a time or to take more than four tablets in a day total. Subjects will be encouraged to spread out the daily dose into at least two doses several hours apart.

This approach to dosing will allow us the flexibility to maintain subject comfort and convenience during study participation.

The active ingredient in MMFS202 (6-hour release) and MMFS302 (12-hour release), L-Threonic acid Magnesium salt has been granted GRAS status by the FDA. Neurocentria produces MMFS202 (6-hour release) and MMFS302 (12-hour release) using good manufacturing practices.

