Subjects who: 1) develop intolerable AE(s) despite dose adjustments; 2) have (a) clinically relevant serious AE(s) as determined by the investigator; 3) have worsening ADHD symptoms (much worse or very much worse as rated on CGI-Improvement at two consecutive visits); or 4) have emergent adverse mental health state including psychosis, suicidality, substance use, or worsening mood and/or anxiety; 5) are non-adherent to study procedures or withdraw from the study; 6) intend to be or become pregnant will no longer continue in the study. If study participation is discontinued due to safety reasons, participants will receive two follow-up visits, giving adequate time for appropriate psychiatric referrals to treaters in their communities.

Subjects found to be taking substances listed as exclusionary during the course of the study may be discontinued based on PI evaluation of their eligibility.

VI. BIOSTATISTICAL ANALYSIS

As this is a single-arm, open study designed to evaluate the effectiveness and safety/tolerability of L-Threonic acid Magnesium salt, formal power analyses are not warranted.

Data processing and management will follow procedures developed by the investigators and used in ongoing studies. 15 subjects will receive L-Threonic acid Magnesium salt. Changes in outcome ratings within and between study groups will be tested. All analyses will be intention to treat (ITT), utilizing.

Our exploratory hypotheses are as follows. Our primary test of Hypothesis 1 will be review of the occurrence of moderate or severe adverse events. Hypothesis 2 will be tested by evaluating whether over the course of L-Threonic acid Magnesium salt administration the following are seen: a) at least a 25% reduction in ADHD as rated by the AISRS total score; b) CGI of much or very much improved, c) reduced symptoms of executive dysfunction (defined by a 0.5 standard deviation improvement on BRIEF-A self-report total or subscale scores). Hypothesis 3 predicts that there will be measurable improvement in cognitive function, as

measured by a) statistically significant improvement on CANTAB tasks, and b) improvement in performance on the WASI matrix, used to estimate IQ, and c) increased correlation between performance on domains of function.

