For ADHD AISRS, BRIEF, and CANTAB evaluations, we will compare pre-treatment and study visit values of measures using paired t-tests, via an intention-to-treat analysis with the last observation carried forward (LOCF) for subjects who did not complete the full study. Alpha will be set at 0.05 for all comparisons.

We will also explore descriptively whether baseline erythrocyte magnesium level, or deficits in BRIEF or CANTAB ratings as measured against norms predict improvement on AISRS or BRIEF ratings.

VII. RISKS AND DISCOMFORTS

All efforts are made to minimize risks to subjects. Consistent with good clinical practice, safety will be monitored by the Principal Investigator, and will reflect the oversight of co-investigator study clinicians. Adverse events will be recorded and reported according to institutional policies. Risks of the study agent have been incorporated into the exclusionary criteria for this proposal.

Study clinician evaluation and subject questionnaires:

Some questions may make subjects feel uncomfortable. Subjects may refuse to answer any question they wish. In the event that a participant reports risk of harm to himself or herself, or to another person, study clinicians will assess the level of risk, and take appropriate actions, including disposition of an immediate referral to a local Psychiatric Emergency Room.

Study Agents –MMF202 (6-hour release) and MMF303 (12-hour release):

The active ingredient in MMF202 (6-hour release) and MMF303 (12-hour release) is L-Threonic acid Magnesium salt, is considered a dietary supplement that the manufacturer has self-certified as fulfilling the US Food and Drug Administration criteria for agents that are Generally Regarded as Safe. There are few risks to taking L-Threonic acid Magnesium salt orally. Magnesium is known to cause gastrointestinal discomfort, nausea, vomiting, or diarrhea. Although occurrences are rare, very large amounts of magnesium might cause hypermagnesemia with symptoms including thirst, hypotension, drowsiness, confusion, loss of tendon reflexes, muscle weakness, respiratory depression, cardiac arrhythmias, coma, cardiac arrest, and death. There have been only two reports of death from hypermagnesemia that we found record of. ⁴³ The dose prescribed to subjects as part of this study will unlikely lead to hypermagnesemia, as extremely high doses of magnesium are required to produce this effect.

ADHD Pharmacotherapies:

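### Kidney dysfunction is excluded because magnesium may accumulate, but no scheduled test measures kidney function, so an unrecognised case could be dosed

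*Combined protocol and SAP*

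**What the plan says.** Section III, exclusion criterion 3, covers known unstable illness in a list of organ systems that includes the kidney. It then adds a separate sentence, with its own safety reason: "Individuals with kidney dysfunction will be excluded, as dysfunctional kidneys may have difficulty clearing the magnesium from the body". A parenthesis explains that magnesium could then rise to a dangerous level. No limit and no method of establishing kidney function is given. The next sentence excludes heart block.

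Section V describes a screening assessment with psychiatric, medical and neuropsychological parts, and states: "The information obtained at this visit will be reviewed to assure that all inclusion and exclusion criteria are met". This review comes before study agent is given at baseline.

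Under Safety Assessments in section V, "We will draw blood samples at the screening visit and at study endpoint"; the analytes are red-cell magnesium and calcium. Also, "For safety purposes, an EKG will be conducted during screening and at the endpoint of the study". The other physical and laboratory tests are vital signs, height, a urine drug screen and, for women able to have children, a urine pregnancy test. The Visual Timeline of Key Study Elements lists the same procedures.

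Under Study Agent and Dosing, "subjects will take up to 2 grams per day of L-Threonic acid Magnesium salt during the course of the study". Section VII states: "Risks of the study agent have been incorporated into the exclusionary criteria for this proposal". It also says of hypermagnesemia: "The dose prescribed to subjects as part of this study will unlikely lead to hypermagnesemia".

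**The concern.** The protocol identifies impaired renal clearance as the route by which this agent could become dangerous, and it names the exclusion criteria as a control on the agent's risks. An exclusion controls a risk only if screening can identify the people it is meant to keep out. Several other criteria have such a measure: an EKG for heart block, a blood pressure limit for hypertension, a pregnancy test, and the WASI-II for IQ. Kidney function has none.

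History and clinical evaluation find recognised or symptomatic disease. A subject with reduced kidney function who does not know of it, and who shows no sign, could satisfy every step of the plan and be dosed. At stake is the safety of that subject, in a study whose first aim is safety.

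**Working it through.** **Step 1: look for a kidney function test.** The protocol states no figure to reproduce, so the check is a reading of each screening and safety procedure.

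| Procedure | When | Measures kidney function? |
|---|---|---|
| Blood pressure, pulse, weight | Every office visit | No |
| Height | Start and end of study | No |
| EKG | Screening, endpoint | No |
| Red-cell magnesium and calcium | Screening, endpoint | No |
| Urine drug screen | Screening, weeks 6 and 12 | No |
| Urine pregnancy test | Screening, weeks 6 and 12 | No |
| Medical history, clinician evaluation | Screening | No; finds recognised disease |

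Count of scheduled kidney function tests: 0 at screening, 0 during treatment, 0 at endpoint.

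**Step 2: see whether another element fills the gap.**
- The general screening protocol described in section III is a phone screen and clinical interviews; no laboratory test is mentioned.
- Section III says other medical records are used only with the subject's written permission, so earlier kidney results would not routinely be seen.
- Section V lets an evaluation by a study clinician within the previous year replace overlapping diagnostic procedures, with a review of the interval history.
- Screening red-cell magnesium is taken before dosing, has no exclusion limit, and is repeated only at week 12 or the drop visit. It cannot show accumulation as it develops.
- The 140/90 mmHg limit and the bans on diuretics and calcium channel blockers may remove some people at higher risk, but only indirectly.

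**Step 3: size, under an assumed rate.** The document gives no rate p of unrecognised kidney dysfunction at ages 18 to 55. I assume 0.1% to 1%. For n, section VI states: "15 subjects will receive L-Threonic acid Magnesium salt". Section V sets a recruitment ceiling of 25.

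Expected cases = n × p. Chance of at least one case = 1 − (1 − p)^n.

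| n | p (assumed) | Expected cases | Chance of at least one |
|---|---|---|---|
| 15 | 0.1% | 15 × 0.001 = 0.015 | 1 − 0.999^15 = 1.5% |
| 15 | 0.5% | 15 × 0.005 = 0.075 | 1 − 0.995^15 = 7.2% |
| 15 | 1% | 15 × 0.01 = 0.15 | 1 − 0.99^15 = 14.0% |
| 25 | 0.1% | 25 × 0.001 = 0.025 | 1 − 0.999^25 = 2.5% |
| 25 | 0.5% | 25 × 0.005 = 0.125 | 1 − 0.995^25 = 11.8% |
| 25 | 1% | 25 × 0.01 = 0.25 | 1 − 0.99^25 = 22.2% |

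The upper figures come from the highest assumed rate. All rows count any unrecognised dysfunction, not dysfunction severe enough to cause harm at this dose. The document does not give the elemental magnesium content of the daily dose, so the step from dysfunction to harm cannot be calculated.

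**The case against.** The best defence is that criterion 3 opens with known illness, so a history-based exclusion was intended and is legitimate. Several other exclusions also have no scheduled test, among them hepatic, thyroid and hematologic illness, recent cancer and narrow-angle glaucoma. Any history-based exclusion can miss an undiagnosed case.

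The plan also has further layers of protection:
- The dose starts at two 0.5 g tablets (1 g/day) for one week, is doubled only if tolerated, and can be reduced later.
- A clinician makes the week 1 call and asks about adverse events; clinicians can be paged at any hour.
- Adverse events and vital signs are checked at weeks 3, 6, 9 and 12, and the principal investigator reviews all events at least monthly.
- With permission, the treaters of subjects already on ADHD medication are contacted before treatment and could report kidney disease.
- Other magnesium products are banned, subjects are no older than 55, and the protocol expects hypermagnesemia only at extremely high doses.

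Much of this stands. It makes an enrolled case less likely, or makes trouble easier to notice, and it is why the point is not graded higher. It does not close the gap. The kidney sentence does not repeat the word known, and among the exclusions without a test it is the one that the protocol ties to dangerous magnesium levels. Step-up dosing and adverse event checks act only after exposure. Section VII lists drowsiness as a symptom of hypermagnesemia, while section I reports passing sleepiness with the agent, so an early sign could be taken as expected. The statement that very high doses are needed does not address impaired clearance.

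**Conclusion.** The concern holds. The protocol excludes kidney dysfunction for a stated safety reason and schedules no test that could detect it, so a subject with unrecognised dysfunction could be dosed without any departure from the plan. The absence of a test rests on the text alone. The probability rests on an assumed rate: at 0.1% to 1%, between 0.015 and 0.15 cases would be expected among 15 treated subjects. The chance that such a case would come to harm is not known from the document and may well be small. The change should be made because the gap concerns the agent's main named hazard and costs little to close; there is no evidence that harm is likely.

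**What to change.** Add serum creatinine with eGFR to the screening blood draw, and add the test to the Visual Timeline of Key Study Elements. Have the study clinicians choose a numerical limit and write it into exclusion criterion 3 before enrolment, so that kidney dysfunction is defined. Review the result with the other eligibility information before the first dose at baseline.

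The cost is one inexpensive assay for at most 25 recruited subjects, with no new visit or needle stick. The protocol does not state the tube type, so an extra tube may be needed. Baseline dosing must wait for the result, and an occasional extra screen failure is possible. No endpoint or analysis changes.

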 - i. Potassium-sparing diuretics such as Amiloride (Midamor), Spironolactone (Aldactone®), and triamterene (Dyrenium®), as they may increase magnesium levels;
 - ii. Loop and thiazide diuretics such as Furosemide (Lasix®) and Hydrodiuril (Microzide ®, Esidrix®, Hydrodiuril®) as they may decrease magnesium levels;

- iii. Muscle relaxants such as Carisoprodol (Soma®), Pipecuronium (Arduan®), Orphenadrine (Banflex®, Disipal®, Norflex ®), Cyclobenzaprine (Flexeril®, Fexmid®, Amrix ®), Gallamine (Flaxedil®), Atracurium (Tracrium®), Pancuronium (Pavulon®), and Succinylcholine (Anectine ®, Quelicin®);
- iv. Penicillamine (Cuprimine®, Depen ®)
- v. Corticosteroids (Prednisone or Deltasone®)
- vi. Magnesium containing antacids including Maalox®, Mylanta®, Milk of Magnesia, Tums® and Rolaids
- d. Supplemental magnesium or any magnesium-containing products
- e. All dietary or herbal supplements or products including those purported to improve memory, improve sleep, or decrease stress.

Any subject found to be taking these substances during the study will be evaluated by the PI for ongoing eligibility.

14. Investigator and his/her immediate family; defined as the investigator's spouse, parent, child, grandparent, or grandchild.

There will be two categories of individuals presenting with ADHD that will participate in the study: (1) those that have residual ADHD symptoms despite benefit from well-tolerated standard of care ADHD pharmacotherapy (stimulant medication or Atomoxetine); and (2) those that are not on medication for ADHD. Because the study is a pilot study, we will recruit a sample of subjects, and have not specified a ratio of participants in these two groups to be enrolled.

No individual will be removed from an effective and stable treatment regimen for the purposes of participating in the study. Individuals who enter the study on medication for ADHD must be on an effective, well tolerated, and stable dose of a prescription indicated by the FDA for ADHD for at least one month prior to entry. Efficacy and tolerability will be determined by the study clinician, and subjects must have a Clinical Global Impression-ADHD severity rating of no greater than 4 ("moderately ill"), because a score greater than 4 indicates that their ADHD symptoms are unlikely to be effectively treated by their current medication regimen.

IV. SUBJECT ENROLLMENT

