We anticipate that subjects may enter this trial following completion of withdrawal from other protocols in our office, and that there may be procedural overlap. So as to not burden subjects with redundant time commitments, we will use the following *diagnostic* data previously collected: If a subject has completed an evaluation with one of the study clinicians within the previous year prior to entrance into this study, they will not be asked to repeat any overlapping diagnostic procedures; if a subject has completed a neuropsychological evaluation within the last 3 months they will not have to repeat this. With subjects' permission, we will use the diagnostic data that had been previously collected. However, the study clinician will review the interval time period to assess for clinically significant medical or psychiatric history, to ensure that the subject meets appropriate study entrance criteria.

Medication Washout:

If clinically appropriate, any subjects taking medication exclusionary to the study must be tapered off this medication prior to baseline visit for the length of 5 half-lives of the medication, corresponding to 95% of the agent leaving the participant's system), plus several days to assess the participant off medication. Discontinuation or taper off of a current medication will be recommended only for subjects with inadequate response to a current treatment. Subjects will not enter the study if it would require tapering a medication that is optimally and comfortably managing a clinical concern. Medication tapers will be monitored by the study clinician in agreement with the research subject and in consultation with the prescribing physician. The prescribing physician will be contacted to discuss feasibility and correctness of removing a subject from current medications and will be asked to monitor the subject's response to the medication change. If the prescribing physician does not find medication discontinuation appropriate or if they do not agree to monitor the subject's response to stopping medications, then the subject will not be enrolled. No subject will be removed from a stable and effective treatment regimen for the purposes of participating in the study.

Participants who fulfill the inclusion and exclusion criteria will participate for 12 weeks, or until withdrawing or terminating participation.

Safety Assessments:

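### Exclusion 13b asks for only 7 days off psychoactive drugs, and the 5-half-life washout does not reach a subject who had already stopped one

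*Combined protocol and SAP*

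**What the plan says.** Exclusion 13 (III. Subject Selection) sets one window for its whole list: "Subjects may not take any of the following substances for at least 7 days prior to baseline and throughout the study". Item 13b places under it "Any psychoactive medications including" antipsychotics, anxiolytics and antidepressants. The same window covers calcium channel blockers (13a), drugs that interact with magnesium (13c), magnesium products (13d) and supplements (13e). One class has a longer rule of its own, in exclusion 11: "Current use of MAO Inhibitor or use within the past two weeks".

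V. Study Procedures, Medication Washout, says that, where clinically appropriate, "any subjects taking medication exclusionary to the study must be tapered off this medication prior to baseline visit". The length is 5 half-lives, described as "corresponding to 95% of the agent leaving" the body, "plus several days to assess the participant off medication". Concomitant Medications / Treatments adds a second rule: when the study asks a subject to come off a CNS-active drug, the interval before baseline is set by the drug's pharmacokinetics and must be long enough for elimination. That section also takes a past and present treatment history at screening. It sends to the PI anyone found on an exclusionary drug during the study or in the seven days before baseline.

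Screening information is "reviewed to assure that all inclusion and exclusion criteria are met prior to receiving study agent at the baseline visit". VI. Biostatistical Analysis compares AISRS, BRIEF and CANTAB with their pre-treatment values by paired t-tests in a single arm.

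**The concern.** The protocol holds two standards for the same drugs, and which one applies depends on why the drug was stopped. A subject tapered for this study must reach 5 half-lives. A subject who stopped the same drug before being assessed need show only 7 days. The rate of elimination is the same in both.

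If a psychoactive drug is still leaving the body when the baseline AISRS and BRIEF-A are rated, part of any later change in that subject may reflect its departure. A pre-post comparison without a control arm cannot separate that from the study agent. With 15 subjects analysed, one subject carries 1/15 = 6.7% of a paired mean change.

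**Working it through.** **Inputs from the documents.** 7 days (exclusion 13); 14 days for MAO inhibitors (exclusion 11); 5 half-lives, said to be 95% eliminated, plus an unspecified several days (Medication Washout); a seven-day look-back (Concomitant Medications / Treatments).

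**Assumptions.** The documents give no half-lives, so 2, 3 and 4 days are used as a range. Elimination is first-order. Several days is taken as 2 to 4 where it is used.

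**1. The plan's own figure.** The share eliminated after k half-lives is 1 − 0.5^k. For k = 5 this is 96.9%, leaving 3.1%. Exactly 95% needs log2(20) = 4.32 half-lives. The stated 95% is therefore a slightly loose description of 5 half-lives, and nothing here turns on the difference.

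**2. Where 7 days falls short.** Seven days equals 5 half-lives at 7/5 = 1.4 days (33.6 h). On the 95% reading it is 7/4.32 = 1.62 days. If the several days count as part of the standard, the cut-off is (7 − 2)/5 = 1.0 day down to (7 − 4)/5 = 0.6 day.

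**3. How far short.** The share left at day d with half-life t is 0.5^(d/t). The shortfall is 5t − 7.

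| Assumed half-life | Left at day 7 | Left at day 8 | 5 half-lives | Shortfall |
|---|---|---|---|---|
| 2 days | 8.8% | 6.3% | 10 days | 3 days |
| 3 days | 19.8% | 15.7% | 15 days | 8 days |
| 4 days | 29.7% | 25.0% | 20 days | 13 days |

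At day 8, more than 10% is left only if the half-life exceeds 8/log2(10) = 2.41 days. On the 95% reading the gap closes earlier, at 4.32t = 8.6, 13.0 and 17.3 days. With 2 to 4 added days it closes later, at 12–14, 17–19 and 22–24 days.

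**4. Who falls in the gap.**

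- A subject on the drug at assessment, or asked to stop it, comes under one of the two washout rules.
- An MAO inhibitor user comes under the two-week rule, which applies whoever stopped the drug and spans 5 half-lives up to 14/5 = 2.8 days.
- A subject who stopped another 13b drug before assessment, more than 7 days but less than 5 half-lives before baseline, comes under neither washout rule. The PI look-back misses this subject too, because it uses the same seven days.

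**The case against.** The best case against is that a flat entry minimum with a pharmacokinetic rule for study-directed tapers is a coherent two-tier design, backed by clinical judgement. Exclusion 3 bars unstable psychiatric illness. A psychiatric assessment and a treatment history come before dosing, AISRS and CGI are rated at both screening and baseline, and eligibility is confirmed at baseline. No 13b drug with a long half-life is named, and at an assumed 2 days the excess is negligible. Individual change in a small open-label pilot is already mixed with time, practice and expectancy. Clearing the drug also does not remove symptom change that continues after treatment stops.

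Much of this stands as a limit on importance. It does not close the gap: each safeguard lets a clinician delay baseline, but none requires it.

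Three stronger readings are tempting, and the documents do not support them.

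- *Adverse events could not be attributed.* The Washout paragraph of VII. Risks and Discomforts has adverse events documented throughout, including any relation to washout.
- *Last-dose dates are not collected.* The 7-day and two-week rules cannot be applied without them.
- *A longer window before baseline would protect every outcome.* It would not protect CANTAB. That test may be done at screening, and a neuropsychological evaluation from the previous 3 months need not be repeated.

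**Conclusion.** The point holds as a minor one. Read literally, 13b admits an otherwise eligible subject who had already stopped a non-MAOI psychoactive drug with a half-life above about 1.4 days, short of the 5 half-lives that the protocol sets for subjects it tapers itself. Under the assumed half-lives of 2 to 4 days the shortfall is up to 3 to 13 days, with 6% to 25% of the drug left at day 8.

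A reader might infer that subjects tapered for the study can also enter at 7 days, or that the results are biased in the agent's favour. Neither follows. Tapered subjects are covered if the longest applicable rule governs. The documents give no basis for the direction or size of a bias, or for the number of subjects affected, which may be zero.

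**What to change.** Word 13b as: at least 7 days or 5 half-lives, whichever is longer, from last dose to baseline, regardless of who stopped the drug or why. Keep 14 days as the minimum for MAO inhibitors, and set the PI look-back for 13b drugs to the same window. If the several days of drug-free observation belong to the standard, state their number and add them to the 5 half-lives.

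For CANTAB, apply the window to the date of the pre-treatment test when it is done at screening or carried over from an earlier evaluation. A test that fails the window would be repeated at baseline.

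The flat 7 days can stay for magnesium antacids, magnesium products and the supplements in 13e ("All dietary or herbal supplements or products including those purported to improve memory, improve sleep, or decrease stress"), which have no single half-life.

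The cost is a sentence in 13b, a phrase in Concomitant Medications / Treatments, a line on CANTAB timing and perhaps an occasional repeat test. No separate last-dose field is needed beyond what the existing rules already require. A few candidates would start later: at most about 3 days at an assumed 2-day half-life and 13 days at 4 days, or 5–7 and 15–17 days if 2 to 4 observation days are added.
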